## **2.2. Endpoints**

### **2.2.1. Primary Endpoint – Efficacy**

#### **Primary Endpoint for Patients with Late-stage HAT**

A patient will be considered as a success, in accordance with the WHO criteria (23), if the patient is alive with no evidence of trypanosomes in any body fluid and a CSF WBC equal to or below 20/ $\mu$ l 18 months after receiving acoziborole.

A patient with no parasitological evidence of a relapse and a CSF WBC above 20/ $\mu$ L or who, in the Investigator's opinion, requires rescue treatment will be considered as a probable relapse.

A patient who refuses the end-of-study lumbar puncture will be classified as a probable cure (success) in the absence of any clinical signs or symptoms suggestive of THA or with another obvious aetiology, provided that the outcome was favourable, i.e. a CSF WBC equal to or below 20/ $\mu$ l, at the last available assessment at 6 months or later.

Death for any reason, patients lost to follow-up and not retrieved or patients who refuse a lumbar puncture at 18 months and who had an unfavourable outcome earlier (probable relapse) will be considered as failures, with the exception of patients who fled the region due to armed conflict or natural disaster. These patients will be replaced by patients from another centre in order to maintain the planned sample size. In order to allow for replacement of some patients lost to follow-up due to armed conflict and to maintain the planned sample size of 155 evaluable patients, 7 additional patients will be enrolled in the study.

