**Table 1 - Clinical Classification of Patients**

Visit	Ideal timing of visit after end of treatment	Favourable outcome	Uncertain outcome	Probable relapse	Proven relapse
D11	$\pm 1$ day	
 
Patient alive with no evidence of trypanosomes in any body fluid (23)
 
			
 
Evidence of trypanosomes in any body fluid
 

3 months	3 months $\pm 1$ week	
 
Patient alive with no evidence of trypanosomes in any body fluid (no lumbar puncture at 3 months unless Investigator suspects a relapse)
 
	
 
Any reason prompting the Investigator to request an additional follow-up visit
 
	
 
Neurological signs or symptoms leading to use of rescue treatment
 
	
 
Evidence of trypanosomes in any body fluid
 

6 months	6 months $\pm 2$ weeks	
 
Patient alive with no evidence of trypanosomes in any body fluid and CSF WBC <math>\leq 20/\mu\text{L}</math>
 
	
 
CSF WBC between 20 and <math>50/\mu\text{L}</math> and additional visit requested within 1-3 months
 
Any reason prompting the Investigator to request an additional follow-up visit
 
	
 
CSF WBC <math>\geq 50/\mu\text{L}</math>
 
Neurological signs or symptoms leading to use of rescue treatment
 
	
 
Evidence of trypanosomes in any body fluid
 

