#### 6.4.4. At Unscheduled Visits

If a relapse of HAT is suspected on the basis of physical examination findings or CSF WBC at any visit, the patient must attend a return visit within 1 to 3 months, at the discretion of the Investigator.

The patient must also return to the investigational centre if s/he does not feel well, even if there is no apparent relationship with treatment or HAT.

The following assessments will be performed:

- Karnofsky performance status;
- Height, weight and BMI;
- Vital signs: body temperature, blood pressure, heart rate, respiratory rate and general status;
- Physical and neurological examinations (including signs and symptoms of HAT since the previous visit);
- Investigation of any concomitant condition that may have led to the visit;
- Testing for *T.b. gambiense* in blood and lymph, if indicated;
- CSF sampling, only if symptoms suggesting relapse are present;
- Laboratory safety assessments at the discretion of the Investigator (see Appendix 3 – Laboratory Tests; p84) – if possible, samples will be collected in the morning from patients in the fasting state:

- Haemoglobin
- Haematology: WBC, platelet count
- Biochemistry: albumin, ALP, ALT, AST, BUN, chloride, creatinine, glucose, potassium, sodium, calcium, total bilirubin, bicarbonates and total protein;
- Thyroid function test, if indicated: TSH, free T3, free T4;
- Additional safety assessments, e.g. ECG or urine analysis, may be performed at the discretion of the Investigator;
- Urine pregnancy test for women of child-bearing potential, at the discretion of the Investigator;
- Collection of concomitant medication and adverse events.

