## 9.8. Handling of Missing Data and Patients Lost to Follow-up

The primary endpoint is the outcome at 18 months. If outcome assessed at the final visit is missing, the **primary imputation method** will consist in imputing a probable success (considered as a success) to patients who attended the 18-month visit, but who refused the lumbar puncture planned at the visit, who showed no signs or symptoms of HAT at 18 months, who did not subsequently report any symptoms of relapse and for whom the outcome was considered as favourable at the last available assessment (17). If these criteria are not fulfilled, the patients will be considered as treatment failures. The outcome for patients who did not attend the 18-month visit or later will also be considered as a failure, except for patients who fled the region due to armed conflict or natural disaster.

Because the historical data may not allow for other imputation methods to be applied, only the primary imputation method will be used. The method will be described in detail in the SAP. Sensitivity analyses will be performed to assess the impact of missing data on acoziborole. The method will be described in detail in the SAP.

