**Table 3 : Time-window for statistical analysis**

| Visit          | Theoretical time    | Time-window |             |
|----------------|---------------------|-------------|-------------|
|                |                     | Lower limit | Upper limit |
| Administration | D1                  | D1          | D1          |
| EoH            | Between D13 and D18 | D2          | D18         |
| 3 months       | D91                 | D19         | D136        |
| 6 months       | D183                | D137        | D273        |
| 12 months      | D365                | D274        | D456        |
| 18 months      | D548                | D457        | D639        |

Note: time-windows described in section 6.1 of the protocol were defined for operational and monitoring activities. They will not be used for statistical analysis.

Note: Time-windows will be applied and calculated visits will be used for the analysis of the following data:

- Vital signs
- Clinical signs and symptoms of HAT
- Physical examination
- Neurological examination
- HAT diagnosis (i.e. examination of blood, lymph and CSF samples)
- Laboratory examination

Time-windows will not be used for calculation of the primary endpoint and secondary endpoints since it is included in the algorithms presented in Sections 10.1 to 10.3. Time-windows will not be used for calculation of the time to proven and definitive failure endpoint since it is included in the algorithm presented in Section 6.3.

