
| Derivation algorithm for stage 1 and intermediate stage (month 18)   | Derivation algorithm for stage 2 (Month 18)  |
|--|--|
| 
Earlier (before M18) unfavorable outcome: increase of WBC in CSF at M6 or M12 with respect to EOH
 
⇒ YES ⇒ 9: Failure (stop)
 
↓
 
NO (no information or no earlier unfavorable assessment)
 
↓
 
Patient has clinical signs or symptoms at M18 evoking a failure
 
⇒ YES ⇒ 10: Failure (stop)
 
↓
 
NO (no clinical signs or symptoms evoking a relapse at M18)
 
↓
 
WBC in CSF ≤ 20 at M12 or absence of LP at M12 and for both cases no increase WBC in CSF at M6 with respect to EOH and no sign and symptoms at M18 evoking a relapse:
 
⇒ YES ⇒ 11: Success (stop) [b]
 
↓
 
NO (at least one criterion not met)
 
↓
 
Patient refused all post treatment lumbar punctures
 
⇒ YES ⇒ 12: Failure (stop) [a,b]
 
↓
 
All other cases ⇒ 13. Failure
 | 
Earlier (before M18) unfavorable outcome: WBC in CSF > 50 at M6 or WBC in CSF > 20 at M12 or increasing between M6 and M12
 
⇒ YES ⇒ 9: Failure (stop)
 
↓
 
NO (no information or no earlier unfavorable assessment)
 
↓
 
Patient has clinical signs or symptoms at M18 evoking a failure
 
⇒ YES ⇒ 10: Failure (stop)
 
↓
 
NO (no clinical signs or symptoms evoking a relapse at M18)
 
↓
 
WBC in CSF ≤ 20 at M12 or in absence of LP at M12 and for both cases WBC in CSF ≤ 50 at M6 and no signs and symptoms at M18 evoking a relapse:
 
⇒ YES ⇒ 11: Success (Stop) [b]
 
↓
 
NO (at least one criterion not met)
 
↓
 
Patient refused all post treatment lumbar punctures
 
⇒ YES ⇒ 12: Failure (Stop) [a,b]
 
↓
 
All other cases ⇒ 13. Failure
 |

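### For late-stage patients with no CSF count at month 18 or later, SAP 10.1 does not read a count from an additional visit between months 6 and 18, although the protocol goes by the last available assessment

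*SAP*

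**What the plan says.** **Protocol.** Section 2.2.1 makes a late-stage patient who refuses the end-of-study puncture a probable cure if there are no signs of the disease and the CSF count was at most 20/µL "at the last available assessment at 6 months or later". Section 9.8 repeats the test for patients who attend M18 but refuse the puncture and "for whom the outcome was considered as favourable at the last available assessment"; those who do not meet it are failures. Neither section limits this to scheduled visits. Section 2.2.1 also says that patients who refuse at M18 and "who had an unfavourable outcome earlier (probable relapse) will be considered as failures".

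The protocol creates extra visits. Table 1 makes an M6 count between 20 and 50 an uncertain outcome, with the words "and additional visit requested within 1-3 months". Section 6.4.4 says that if relapse is suspected "the patient must attend a return visit within 1 to 3 months".

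**SAP.** In the stage 2 column of 10.1, a patient who reaches box 9 has no reliable count at M18 or later.
- Box 9 gives Failure for more than 50 cells at M6, more than 20 at M12, "at M12 or increasing between M6 and M12" being its last words.
- Box 11 gives Success if M12 is at most 20 or there was no M12 puncture, provided M6 is at most 50 and there are no signs at M18.
- Boxes 7 and 8 admit an additional visit only when its count comes later than M18.

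Section 8.10 brings unscheduled visits into the analysis through the time-windows and otherwise only lists them. The notes to Table 3 in 7.5 say "Time-windows will not be used for calculation of the primary endpoint and secondary endpoints since it is included in the algorithms".

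**The concern.** A cell count taken because relapse was suspected is the most informative result available for a patient who then declines the M18 puncture. SAP 10.1 has no step that reads it, and the windowing that could have placed it in a visit slot is switched off on the ground that the algorithms already contain it. The 10.1 algorithm contains no such rule. Section 6.1 has a committee check each patient's status before lock, but with the same algorithm. Section 11 does not list this as a change from the protocol.

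At stake is a false success in the primary endpoint, and less clearly a false failure. Protocol 9.6.2 rests interpretation on the observed rate and the lower 95% bound. None of the six sensitivity analyses in SAP 8.6.1.2 reads the unread count: three change only the analysis set, the fair-case method resamples box 11, the best-case method leaves box 11 as Success, and the observed-case method sets the outcome to missing.

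**Working it through.** **1. Example patients.** All are late-stage, alive, without rescue or trypanosomes, not lost to follow-up, with no signs at M18 and no reliable count at M18 or later. Counts are per µL. The protocol column applies the last-available rule of 2.2.1 and 9.8.

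| Patient | SAP 10.1, stage 2 | Protocol |
|---|---|---|
| A: M6 18, M12 12, month 15 45 | Box 9 not met; box 11 Success | Last count above 20: not a probable cure |
| B: M6 10, no M12 puncture, month 14 60 | Box 9 not met; box 11 Success | Last count above 20: not a probable cure |
| C: M6 45, M12 30, month 14 10 | M12 above 20: box 9 Failure | Last count at most 20: probable cure |

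In patient C no earlier result is a probable relapse. Table 1 calls the M6 count uncertain and the M12 count favourable, because it lies between 20 and 50 and has fallen.

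**2. The SAP against itself.** Take patient B through SAP 10.2. With no reliable M12 count, that algorithm turns to a later count, from M18 or another additional visit. The month-14 count of 60 exceeds 20, so box 8 gives Failure at M12. In 10.1 the same patient is a Success at M18. This does not depend on how the protocol is read.

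**3. What the windows would have done.** Month 14 is about day 14 × 365/12 ≈ 426. SAP Table 3 gives the M12 window as D274 to D456, with the latest visit in a window used. Had windows applied, patient B's M12 count would be 60 and box 9 would give Failure.

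**4. Size per patient.** The Jeffreys interval is the 2.5% and 97.5% quantiles of Beta(x + 0.5, n − x + 0.5). For x = 138 and n = 155 this gives 83.4% to 93.2%, width 9.8, which reproduces the figure in protocol 9.1. One patient is 1/155 = 0.65 points.

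| Successes of 155 | Rate | Lower bound |
|---|---|---|
| 138 | 89.0% | 83.4% |
| 137 | 88.4% | 82.6% |
| 135 | 87.1% | 81.2% |

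**5. How many.** The documents give no frequency. Suppose, purely as an assumption, that 5–10% of patients have no reliable count at M18 or later, and that 5–20% of these had a puncture at an additional visit. Then 155 × 0.05 × 0.05 = 0.4 to 155 × 0.10 × 0.20 = 3.1 patients have such a count at all. Only some of them would change class.

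**The case against.** The case for leaving 10.1 alone has several parts, and most of them stand as limits on scope.

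- **Suspected relapses are not ignored.** A reader might infer that a puncture done on suspicion never reaches the primary outcome. That is not so. Rescue (box 2) or trypanosomes at any time up to M18 (box 3) give Failure, and a reliable count at M18 or later decides in boxes 5 to 8. Only a cell count goes unread, and only when no such later count exists.
- **A high M6 count followed by a normal recall.** With M6 60 and a month-8 count of 10, a reader might infer that box 9 wrongly fails the patient. The documents do not support this. Table 1 makes 50 or more at M6 a probable relapse, and 2.2.1 fails refusers with one. The two sentences in 2.2.1 conflict here, and box 9 follows one of them.
- **Early and intermediate stage.** A reader might extend the point to the left-hand column. Protocol 2.2.2 says that without an 18-month puncture the 6- or 12-month outcome is used for that cohort, so that column is consistent with it in reading only those visits.
- **Few such punctures.** Section 6.4.4 takes CSF at unscheduled visits only with symptoms suggesting relapse. That sits awkwardly with the recall in Table 1 for a cell count alone, and the two must be reconciled; as written, it keeps numbers small.
- **Reading of box 9 and Table 1.** The last clause of box 9 might be stretched to a rise seen at a visit between M6 and M12. It cannot reach counts after M12, as in patients A and B. The 18-month row of Table 1 calls a well patient who refuses puncture favourable on the investigator's judgement, but 2.2.1 and 9.8 define the endpoint and add the last-count condition.

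None of this supplies a rule for patients A and B.

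**Conclusion.** The gap is real, narrow and minor. It is confined to the stage 2 column of SAP 10.1 and to patients with no reliable count at M18 or later, no rescue and no trypanosomes. For them a reliable count from an additional visit between M6 and M18 goes unread, contrary to protocol 2.2.1 and 9.8 and out of line with SAP 10.2. The clear error is a false success. A false failure is possible only where the earlier raised count was not a probable relapse in Table 1, as in patient C.

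Each affected patient moves the rate by 0.65 points and the lower bound by about 0.8. It is tempting to read the assumed 0.4 to 3.1 patients as an error of up to about 2 points. The documents do not support that: the percentages are assumptions, a recall count that agrees with the scheduled ones changes nothing, and errors in opposite directions offset. The likely effect is none or very few patients.

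**What to change.** In the stage 2 column of SAP 10.1 only:

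1. Keep the existing M6 and M12 tests. Insert a step before box 11: if the latest reliable (non-haemorrhagic) CSF count before M18 comes from an additional visit at 6 months or later and is above 20, the outcome is Failure. State whether the new box carries the [a] or [b] mark; box 9 carries neither.
2. For a latest additional-visit count of at most 20 after an earlier raised count, reconcile the two sentences in protocol 2.2.1, on the last available assessment and on an earlier probable relapse, and state which governs box 9.
3. In 7.5, replace the note that windows are included in the algorithms with a statement of how additional visits before M18 are handled.
4. List any remaining departure from the protocol in section 11.

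Boxes 9 and 11 should not be replaced outright by a single latest-count rule. That would reclassify patients who had no additional visit: M6 60 with M12 10, and M6 5 with M12 15, would turn from Failure to Success, and M6 30 with no M12 puncture from Success to Failure.

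The cost is SAP wording and one added condition in the two independent programs for the primary endpoint. Protocol 6.1 already has unscheduled visits recorded in the CRF, and SAP 8.10 already lists them.

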12 months	12 months $\pm 4$ weeks	
 
Patient alive with no evidence of trypanosomes in any body fluid and CSF WBC <math>\leq 20/\mu\text{L}</math>
 
CSF WBC between 20 and <math>50/\mu\text{L}</math>, and lower as compared to prior value(s)
 
	
 
CSF WBC <math>> 20/\mu\text{L}</math> and non-significant increase from a clinical standpoint in relation to prior value(s)
 
Any reason prompting the Investigator to request an additional follow-up visit
 
	
 
CSF WBC <math>> 20/\mu\text{L}</math> and significant increase from a clinical standpoint in relation to prior value(s)
 
Neurological signs or symptoms leading to use of rescue treatment
 
	
 
Evidence of trypanosomes in any body fluid
 

18 months	18 months $\pm 4$ weeks	
 
Patient alive with no evidence of trypanosomes in any body fluid and CSF WBC <math>\leq 20/\mu\text{L}</math>
 
Patient with no signs of HAT and who refuses to undergo lumbar puncture and who, in the opinion of the Investigator does not require rescue treatment or an additional follow-up visit
 
	
 
Any reason prompting the Investigator to request an additional follow-up visit
 
	
 
CSF WBC <math>> 20/\mu\text{L}</math>
 
Neurological signs or symptoms leading to use of rescue treatment
 
	
 
Evidence of trypanosomes in any body fluid
 

Any discrepancy between the clinical features and laboratory findings may also be an uncertain outcome, or any situation that leads the Investigator or the study team to consider that an additional follow-up visit is required to decide whether or not to provide rescue treatment.

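### For stage 2 patients who refuse the month-18 lumbar puncture, SAP 10.1 reverses the protocol's primary-endpoint class in two groups, and SAP Section 11 does not declare it.

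*SAP*

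**What the plan says.** **Protocol.** Section 2.2.1 treats a sign-free patient who refuses the final lumbar puncture as a probable cure if the CSF count was 20/µL or less "at the last available assessment at 6 months or later". It also says that refusers "who had an unfavourable outcome earlier (probable relapse) will be considered as failures". Section 9.8 repeats the rule as the primary imputation method and sets the default: "If these criteria are not fulfilled, the patients will be considered as treatment failures". It adds: "The outcome for patients who did not attend the 18-month visit or later will also be considered as a failure", apart from patients who fled conflict or disaster.

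**SAP 10.1, stage 2 column**, for patients with no reliable count at month 18 (M18) or later:

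- Step 4 fails a patient lost to follow-up, described there as having no survival information at M18 or later. SAP 7.7 derives the same status from a tick box on the End of Study form.
- Step 9 fails a count above 50 at M6, a count above 20 at M12, or any rise between the two.
- Step 11 gives success if M12 is at or below 20 or, "in absence of LP at M12 and for both cases WBC in CSF ≤ 50 at M6", provided there are no signs at M18.
- Step 13 fails everyone left over.

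**SAP Section 11** lists three changes from the protocol: adverse-event counting, stage wording and the NECT yardstick.

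**The concern.** The SAP says that it is based on protocol version 4.0, so a difference between versions does not explain the mismatch. Protocol 9.8 leaves detail to the SAP, but giving the opposite class to a patient whom the protocol has already classified is more than detail.

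This is the primary endpoint of a single-arm trial with no formal success rule. Interpretation rests on the observed rate and its lower 95% bound, read against NECT (SAP Table 4 total 94.1%, interval 91.4% to 96.2%). A reader who takes the endpoint from the protocol would be looking at a rate derived by a different rule, without being told.

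**Working it through.** **1. The plan's own intervals.** The Jeffreys limits are the 2.5% and 97.5% quantiles of Beta(x + 0.5, n − x + 0.5).

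- 138/155 = 89.0%: 83.4% to 93.2%, as in protocol 9.1.
- 146/155 = 94.2%: 89.7% to 97.1%, as in protocol 9.1.
- NECT total 354/376: 91.4% to 96.2%, as in SAP Table 4.

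**2. Example patients.** Each is alive, with no rescue treatment, no trypanosomes and no signs, attends M18, refuses the puncture and has no later count.

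| M6 | M12 | Protocol 2.2.1 and 9.8 | SAP 10.1 |
|---|---|---|---|
| 35 | none | last count 35: Failure | step 11: Success |
| 5 | 10 | last count 10: Success | step 9 (rise): Failure |
| none | 5 | last count 5: Success | step 13: Failure, if a missing M6 count does not meet the limit of 50 |

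**3. Full trace.** M6 and M12 each took the values 0 to 100 or missing, giving 102 × 102 = 10,404 histories. SAP 10.1 was compared with three readings of the protocol:

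- R1: the last count at M6 or later is 20 or less (2.2.1).
- R2: R1, plus failure for an earlier probable relapse (2.2.1, with the Table 1 threshold of 50 or more at M6).
- R3: favourable at the last assessment as in the M6 and M12 rows of Table 1 (9.8).

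All three readings agree with each other and contradict the SAP in these patterns:

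- (a) M6 21 to 50, M12 missing: 30 histories. SAP Success, protocol Failure.
- (b) M6 below M12, M12 at or below 20: 210 histories. SAP Failure, protocol Success.
- Third pattern, M6 missing and M12 at or below 20: 21 histories. SAP Failure, protocol Success. All 21 disappear if a missing M6 count is not held against the patient at step 11.

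These counts check the logic and are not patient frequencies. The trace covers only the scheduled M6 and M12 counts, not counts from unscheduled visits.

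**4. Consistency within the SAP.**

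- The patient in (a) is a Failure at M6 (10.3 step 7, count 21 to 50 with no further puncture) and at M12 (10.2 step 12, M6 above 20), then a Success at M18 on no new CSF data.
- For (b), M6 above 50 or M12 above 20 already fails at step 9. The rise clause can therefore change a result only when M6 < M12 ≤ 20, which is a protocol success. At M12 the SAP uses a rise only for counts above 20 (10.2 step 6).

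**5. Size per patient at n = 155.** The rate moves by 1/155 = 0.65 points. Lower bounds are 88.1% at 144 successes, 88.9% at 145, 89.7% at 146, 90.5% at 147, 93.1% at 150 and 94.0% at 151, so each patient moves the bound by about 0.8 to 0.9 points.

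As an illustration, assume a net shift of up to 3 patients either way:

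- From 146/155: between 143/155 = 92.3% (lower bound 87.3%) and 149/155 = 96.1% (92.2%).
- From 138/155: between 135/155 = 87.1% (81.1%) and 141/155 = 91.0% (85.7%).

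**The case against.** **The protocol is not uniform.** The M18 row of Table 1 lists as favourable a "Patient with no signs of HAT and who refuses to undergo lumbar puncture", if the investigator sees no need for rescue treatment or a further visit, with no condition on earlier counts. That would support the SAP on (a). The clause in 2.2.1 that fails refusers outright concerns probable relapse, and an M6 count of 20 to 50 is only uncertain in Table 1 ("and additional visit requested within 1-3 months"). This stands as a conflict to reconcile. It does not rescue the SAP: the same row would make (b) a success, and 2.2.1 and 9.8, not the rescue-treatment table in 5.4, define the endpoint and its imputation.

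**The SAP gave notice.** SAP 6.1 speaks of adapted WHO criteria and has a committee check each patient's status before lock. But it names no adaptation, and the committee applies this same algorithm.

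**A reader might count three reversals.** The third needs a missing M6 count to fail the limit of 50. The SAP does not say so, and the exit from step 9 lets missing information pass. It is an ambiguity.

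**A reader might infer that fair case resampling misses (b) and the third pattern**, because mark [b] is on steps 4, 11 and 12 only. The third bullet of the fair case method in SAP 7.6.1 covers patients without a count at the visit and without proven success at another visit, which may include them. Text and marks disagree. The observed case method also sets these patients to missing.

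**A reader might infer that patients who withdraw after M6 become successes.** That happens only if signs never assessed at M18 are read as absent. Otherwise step 13 fails them, as 9.8 does.

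**Conclusion.** The SAP is wrong as written for (a) and (b). On the literal text of steps 9 and 11 it gives the opposite class to protocol 2.2.1 and 9.8, and Section 11 does not declare it. No planned analysis applies the protocol rule itself. The third pattern and the handling of missing M6 counts need a stated rule.

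This should be fixed, but the documents do not show that it threatens the trial's conclusion. The number of patients affected is not given. Group (a) makes the SAP more lenient and (b) makes it stricter, so the net direction is unknown.

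One patient separates 146/155 = 94.2% from 145/155 = 93.5%, either side of the NECT total, and a reader might infer that this decides the result. With no formal success rule, the NECT total is a yardstick and not a threshold.

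**What to change.** 1. **Step 11:** require that the last reliable CSF count at M6 or later is 20/µL or less, with no M6 count needed when M12 is available, and with signs assessed and absent at an attended visit at M18 or later.
2. **Step 9:** remove the rise between M6 and M12 as a ground for failure when both counts are 20 or less.
3. **Step 4 and SAP 7.7:** match protocol 9.8, so that a patient not seen at M18 or later is a failure whatever the recorded reason, except those removed by the mITT definition.
4. **Sensitivity and disclosure:** keep the present algorithm as a labelled sensitivity analysis, reconcile the fair case text with the [b] marks, and declare in Section 11 any departure that is kept.
5. **Protocol Table 1:** reconcile with 2.2.1 both the M18 row on sign-free refusers and the M12 row, which calls a count of 20 to 50 "and lower as compared to prior value(s") favourable.

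The cost is a few lines of SAP text and derivation code. The primary rate may move slightly in either direction.
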